#### *F) Statistical analysis*

Data will be presented as mean and standard deviation for continuous variables, and frequency and percentage for categorical variables. For the a priori defined ultrasound outcomes of PIS, diastolic dysfunction, and increased ONSD, the prevalence and 95% confidence intervals will be calculated. In addition, the prevalence and 95% confidence intervals of systolic dysfunction and of raised LVEDP will be calculated.

Patients with and without ultrasound abnormalities will be compared with respect to admission systolic and diastolic blood pressures, clinical features of disease severity, and mean BNP levels using 2-sample t-test and the Chi-square test, for continuous and categorical variables respectively. The associations between PIS, increased ONSD or diastolic dysfunction with clinical severity features (=high arterial blood pressures, presence of pulmonary edema, headaches or visual disturbances, raised liver or renal laboratory parameters tests, and low platelet count), serum albumin level, BNP level, and between cardiac and pulmonary ultrasound abnormalities, will be explored using the 2-sample t-test and the Chi-square test, for categorical and continuous variables respectively. To adjust for multiple comparisons, including primary and secondary outcomes, a Benjamini-Hochberg correction will be applied using a 10% false discovery rate. Assuming that the p-value will result from 32 direct comparisons made in the study, the significance level will be adjusted to  $p < 0.025$ .

In order to determine pre- and post-test probabilities of PIS to predict elevated LVEDP, and of BNP at a level above 200 pg/ml to predict systolic dysfunction, diastolic dysfunction, elevated LVEDP, and the presence of PIS, sensitivity, specificity, positive and negative predictive value will be calculated.

Intra- and inter-observer agreement will be evaluated using the Bland and Altman method, after reviewing 10% of lung- (using total B-line score), cardiac- (using left ventricular internal diameter in diastole (LVEDD), and optic nerve (using the left optic nerve sheath

diameter) parameters; results will be expressed both graphically and quantitatively as mean difference (bias) and 95% limits of agreement.

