#### *Sample size calculation*

The sample size calculation is based upon the primary aim, which is to examine the association between PIS on lung ultrasound and raised LVEDP on cardiac ultrasound. Available data on women with late onset preeclampsia and severe features suggest that the incidences of PIS and raised LVEDP are 23/95 (24%; 95% CI: 16-34%), and 20/80 (25%; 95% CI: 16-36%) respectively. In that population, the proportion of women with raised LVEDP was 12% in patients without PIS, and 55% in those who had PIS. A sample size of 60 (45 LVEDP negative and 15 LVEDP positive) will be required to detect a significant difference in incidence of PIS between the 2 groups (52% [expected PIS positive rate in women with raised LVEDP] versus 15% [expected PIS positive rate in women with normal LVEDP]) with a power of 80% and significance level of 0.05. To allow for the possibility of poor image acquisition during positive pressure ventilation, 70 patients will be recruited.

[figure not shown]

Figure 1: Comparison of normal lung in Panel A versus B-line pattern in Panel B.

[figure not shown]

Figure 2 (Image from Ref.): Measurement of the optic nerve sheath diameter in the coronal axis. The view is obtained in a sharply demarcated circle, measured in its widest diameter (A). If edema is seen, the measurement is taken at the outer edge (B, outer calipers).

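### Chi-square is the only test named for categorical comparisons, with no small-count rule; in sparse secondary tables its p-values can be too small at the early Benjamini-Hochberg steps

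*Combined protocol and SAP*

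**What the plan says.** Section F) Statistical analysis names two tests. Women with and without ultrasound abnormalities are to be compared on blood pressures, "clinical features of disease severity, and mean BNP levels using 2-sample t-test and the Chi-square test", the first test being for continuous and the second for categorical variables. For the associations of pulmonary interstitial syndrome (PIS), increased optic nerve sheath diameter or diastolic dysfunction with severity, albumin and BNP, and between cardiac and lung findings, the analysis "will be explored using the 2-sample t-test and the Chi-square test, for categorical and continuous variables respectively". The variable types are reversed in that second sentence, evidently a slip. Chi-square is therefore the only test for categorical data, and neither sentence provides for small counts.

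The severity features, besides high blood pressure, are "presence of pulmonary edema, headaches or visual disturbances, raised liver or renal laboratory parameters tests, and low platelet count". No prevalence is given for any of them in eclampsia.

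On multiplicity, "a Benjamini-Hochberg correction will be applied using a 10% false discovery rate", covering primary and secondary outcomes. The section continues: "Assuming that the p-value will result from 32 direct comparisons made in the study, the significance level will be adjusted to" p < 0.025.

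Under Sample size calculation, "A sample size of 60 (45 LVEDP negative and 15 LVEDP positive) will be required" for 80% power at 0.05, with PIS rates of 52% and 15%; 70 women are to be recruited.

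**The concern.** Pearson's chi-square p-value is a large-sample approximation. When an expected count is well below 5 it can be much too small, most of all in the far tail. Benjamini-Hochberg uses that tail: its cut-offs start at 0.10/32 = 0.0031. One or two affected women in a small group could then yield a p-value that passes the strictest step, and the 10% false discovery rate would not hold for the secondary associations. With a smaller group of 15, any feature present in fewer than one third of all women gives an expected count below 5 (15 × 1/3 = 5), so the situation is not exotic.

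**Working it through.** **The plan's own figure.** With p1 = 0.52, p2 = 0.15 and a 1:3 split, the pooled rate is (0.52 + 3 × 0.15)/4 = 0.2425. The two-sided formula without continuity correction is

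n1 = [1.96·√((4/3)·0.2425·0.7575) + 0.8416·√(0.52·0.48 + 0.15·0.85/3)]² / 0.37² = (0.970 + 0.455)² / 0.1369 = 14.8, rounded up to 15.

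This gives 15 + 45 = 60, as planned.

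**Benjamini-Hochberg levels.** Step k is k × 0.10/32: 0.0031 at k = 1, 0.025 at k = 8 (the plan's stated level) and 0.10 at k = 32.

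**Two single tables by hand**, using X² = N(ad − bc)²/(product of the four margins):

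- 3/15 versus 0/45: X² = 60 × (3 × 45)²/(15 × 45 × 3 × 57) = 9.47, p = 0.0021. Fisher: C(15,3)/C(60,3) = 455/34,220 = 0.0133. Mid-p is half of that, about 0.0066.
- 1/6 versus 0/54: X² = 60 × 54²/(6 × 54 × 1 × 59) = 9.15, p = 0.0025. Fisher: 6/60 = 0.100. Mid-p = 0.050.

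Mid-p here is the two-sided Fisher p-value minus half the probability of the observed table.

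**Exact size.** For a common feature rate p, size(α) is the sum over all (x, y) of Bin(x; n1, p) × Bin(y; n2, p) wherever the table's p-value is at most α. Only the 15/45 split is planned. The smaller groups and the 3-10% feature rates are assumptions.

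| Split | Pearson size at 0.0031 | Ratio to nominal | Ratio at 0.025 |
|---|---|---|---|
| 3 / 57 | 0.019-0.044 | 6-14 | up to 2.8 |
| 5 / 55 | 0.011-0.032 | 3.6-10 | up to about 1.4 |
| 10 / 50 | 0.007-0.010 | 2.2-3.0 | up to 2.8 |
| 15 / 45 | 0.003-0.006 | 0.9-2.0 | 0.9-1.1 |

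At 15/45 the peak at step 1 is at a rate of 8%. At 14/46 (a PIS rate of 24% in 60 women) the ratio reaches 1.8 at 0.0125 for a 5% feature. Mid-p is below nominal in every cell of the table.

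**Primary table.** Its smallest expected count is 15 × (15 × 0.52 + 45 × 0.15)/60 = 3.6. At a null rate of 24%, Pearson's size is 0.054 at 0.05, 0.022 at 0.025 and 0.0027 at 0.0031.

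**False discovery rate.** This was simulated with all 32 null hypotheses true, 12 tables sparse with a 5% feature rate, the other 20 p-values uniform, all independent, in 20,000 runs. Pearson gives 39% for 3/57, 31% for 6/54 and 12% for 15/45, against the nominal 10%. Mid-p gives 7.5-8.5%.

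**The case against.** The strongest reply is that the large multiples come from inputs the documents do not supply. The documented rates, 24% for PIS and 25% for raised LVEDP, imply groups of 14 or 15 among 60, where the excess is at most about twofold at the first step and negligible at 0.025. Systolic dysfunction, the natural candidate for a tiny group, is assigned a prevalence and BNP accuracy measures; it enters a significance test only if the general reference to ultrasound abnormalities is read broadly. The first step decides the result only when nothing else is rejected, and the levels rise to 0.10. The associations are described as exploratory. All of this stands and limits the point's weight. It does not remove the gap: a split of 10 versus 50 is within the plan's own uncertainty (the lower confidence limit of 16% for both rates gives 0.16 × 60 = 9.6 women), and a fallback rule acts only if sparse tables occur.

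Three stronger readings are tempting, and the documents support none of them:

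- **The primary result is compromised.** It is not; its size is close to nominal at each level checked.
- **The false discovery rate will exceed 10%.** That depends on feature rates and group sizes not given. At 15/45 with a null rate of 24% in the 12 tables, the same simulation gives 9.7%.
- **Mid-p could replace chi-square everywhere and keep 80% power.** On the primary table, exact power at 0.05 is 83.0% for Pearson and 80.2% for this mid-p, but only 77.1% for the version that doubles a one-sided mid-p. At 0.025 Pearson has 72.2% and mid-p 71.0%, so neither reaches 80%. That mismatch between the design level and the adjusted level is a separate matter.

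**Conclusion.** The point holds as a minor gap confined to sparse secondary tables. Chi-square is prescribed without a small-count rule, and where a group is very small and a feature uncommon its p-values are several times too small at the first Benjamini-Hochberg steps. The size of the problem runs from negligible to about 14-fold, depending on group size and feature rate. The lower end applies at the planned split; the upper end needs groups of about three women, which is an assumption. Individual p-values at 15/45 can still be about three times too small against mid-p (0.0021 versus 0.0066 for 3/15 versus 0/45). The primary analysis needs no change on this account.

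**What to change.** Add to F) Statistical analysis: *For any secondary 2x2 table with an expected count below 5, the two-sided mid-p exact test (two-sided Fisher p-value minus half the probability of the observed table) replaces the chi-square test, and that p-value enters the Benjamini-Hochberg procedure.* Keep chi-square for the primary PIS-by-LVEDP table, and correct the reversed variable types in the association sentence at the same time.

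The cost is one sentence and a short calculation. Power is slightly lower in sparse secondary tables. Mid-p does not strictly guarantee the nominal level: over the splits and rates tried, its worst case was about 1.26 times nominal (4 versus 56, rate 50%, level 0.025). If a strict guarantee is preferred, Fisher's exact test provides it at a higher cost in power.

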
Cardiopulmonary and optic nerve sheath point-of-care ultrasound (POCUS) protocols might be particularly suitable for this purpose. These involve a defined bedside ultrasound examination to identify critical cardiopulmonary pathophysiology, which may remain undetected by clinical examination alone. The identification of increased optic nerve sheath diameter (ONSD) on ultrasound may suggest raised ICP.

It is further well documented that the serum brain natriuretic peptide (BNP) level, a marker of cardiac dysfunction, is increased in preeclampsia. However, no data is available to confirm that elevated BNP levels identify those eclamptic women at risk for cardiopulmonary abnormalities.

Therefore, this study is planned to describe the prevalence and severity of cardiac, lung and ONS US abnormalities in women with eclampsia. In a recent study on POCUS findings in late onset preeclampsia, the absence of pulmonary interstitial syndrome (PIS) may exclude raised LVEDP. The **primary aim** of the current study is to examine the association between PIS, as identified by lung ultrasound, and cardiac dysfunction on echocardiography, in eclamptic women. The **secondary aims** are the performance of a comprehensive cardiac ultrasound assessment including a strain analysis, and to explore the association between PIS and ONSD, serum BNP and albumin.

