will be measured 3 mm behind the globe in a perpendicular axis to the nerve (Figure 3). Two measurements will be taken per eye, and the mean of the 4 values will represent the optic nerve sheath diameter.

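### Section F tests optic nerve sheath diameter (ONSD) only as a yes/no finding although it is measured on a continuous scale, and lists no PIS–ONSD comparison although that is a secondary aim (minor)

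*Combined protocol and SAP*

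**What the plan says.** The secondary aims in the Introduction include "to explore the association between PIS and ONSD, serum BNP and albumin". ONSD stands there without the word increased, next to two laboratory values.

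Section Ec takes two readings per eye, and "the mean of the 4 values will represent the optic nerve sheath diameter". The result is a continuous variable.

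Section F uses ONSD in three places:

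- **Prevalence:** "For the a priori defined ultrasound outcomes of PIS, diastolic dysfunction, and increased ONSD", a prevalence with 95% confidence interval is planned.
- **Associations:** the list opens with "The associations between PIS, increased ONSD or diastolic dysfunction with clinical severity features" and goes on to albumin and BNP. The only pair of ultrasound findings in the list comes at its end: "and between cardiac and pulmonary ultrasound abnormalities, will be explored using the 2-sample t-test and the Chi-square test".
- **Observer agreement:** the left-eye diameter is used on its continuous scale in the Bland–Altman analysis, which is not an association test.

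On multiplicity, Section F says "Assuming that the p-value will result from 32 direct comparisons made in the study, the significance level will be adjusted to" p < 0.025. The comparisons that make up the 32 are not itemised.

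**The concern.** There are two separate gaps.

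1. The listed tests of ONSD against albumin, BNP and the severity features use a two-category version of a variable that is available as a measurement. All patients on the same side of the cut-off are treated as equal, so information already collected is left unused.
2. The secondary aim has three parts. PIS–BNP and PIS–albumin are covered by the association list. PIS–ONSD is not: ONSD is not a severity feature, and it is neither a cardiac nor a pulmonary abnormality. That part of the aim has no listed test, and the form of ONSD to be used is not stated.

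At this sample size a real association involving ONSD would be missed more often than necessary and might be read as absent. Where the form is open, the yes/no or the continuous result could also be chosen after the data are seen. Neither gap depends on which cut-off defines increased ONSD.

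**Working it through.** **The plan's own figure.** The plan states "A sample size of 60 (45 LVEDP negative and 15 LVEDP positive) will be required", for PIS rates of 52% versus 15%, 80% power and a 0.05 level. With pooled variance, two-sided, ratio 3:1 and no continuity correction, the pooled rate is (15×0.52 + 45×0.15)/60 = 0.2425, and

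n₁ = [1.960·√(0.2425×0.7575×4/3) + 0.842·√(0.52×0.48 + 0.15×0.85/3)]² / 0.37² = 14.8, rounded up to 15.

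So 15 + 45 = 60 reproduces. It was set for the primary aim; the documents contain no power calculation for ONSD.

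**Inputs for ONSD**

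- N = 60 (Sample size calculation).
- Level 0.025 (Section F), taken as two-sided.
- PIS rate 23/95 (Sample size calculation), so 60×23/95 = 14.5 PIS-positive, taken as 15 versus 45.
- Assumed, because the documents give no figure: normality with equal SD, 10–50% of patients with increased ONSD, and the effect sizes shown.

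**Step 1: listed tests against albumin and BNP.** If a fraction p lies above the cut-off and z is the matching normal quantile, the share of information kept is φ(z)²/[p(1−p)]. A correlation r shrinks to r times the square root of that share. Power by Fisher's z is Φ(atanh(r)·√57 − 2.241). With continuous ONSD and r = 0.4 this is Φ(3.198 − 2.241) = 83%. In yes/no form:

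| Increased ONSD | Share kept | 60 patients worth | r becomes | Power |
|---|---|---|---|---|
| 10% | 0.342 | 20.5 | 0.234 | 33% |
| 20% | 0.490 | 29.4 | 0.280 | 47% |
| 30% | 0.576 | 34.5 | 0.304 | 55% |
| 40% | 0.622 | 37.3 | 0.315 | 59% |
| 50% | 0.637 | 38.2 | 0.319 | 60% |

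The share kept does not depend on the assumed correlation; the power figures do.

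**Step 2: PIS–ONSD, as a conditional illustration only.** For continuous ONSD, the t-test has 58 degrees of freedom and noncentrality d·√(15×45/60) = 3.354d. For the yes/no form, the cut-off c solves [15·P(Z > c−d) + 45·P(Z > c)]/60 = p, and the power of the uncorrected chi-square test is found by enumerating both binomials. At d = 0.8 and p = 30%, for example, the rates of increased ONSD are 52.0% versus 22.7% and the power is 47.2%.

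| Assumed difference | Continuous (t-test) | Yes/no (chi-square), p = 10–50% |
|---|---|---|
| 0.6 SD | 39% | 24–28% |
| 0.8 SD | 65% | 39–47% |
| 1.0 SD | 85% | 55–67% |

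Sensitivity at 0.8 SD:

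- At a 0.05 level: 75% versus 45–59%.
- With 10 or 20 PIS-positive patients (about the 16% and 34% confidence limits in the plan): 51% versus 30–39%, and 73% versus 41–53%.
- With 70 patients (17 versus 53): 72% versus 42–53%.
- With Yates' correction or Fisher's exact test, at 15–50% prevalence, the yes/no figure is about 27–40%.

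**Step 3: precision with continuous ONSD.** The 95% CI half-width for the mean difference is t(0.975, 58)·√(1/15 + 1/45) = 0.60 SD.

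**The case against.** A reader might infer that the plan commits the PIS–ONSD aim to a yes/no test with 39–47% power. The documents do not support that. No such test is listed, the aim names plain ONSD, and Section F provides a two-sample t-test that could be applied to the continuous mean. Carrying the yes/no form over to this pair is an inference from how Section F treats ONSD elsewhere. This part of the objection stands: for PIS–ONSD the omission is missing detail, and the power loss is hypothetical.

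The yes/no form is also a defensible choice. The Introduction presents an increased diameter as a sign of raised intracranial pressure, and Section F treats its three a priori ultrasound outcomes alike, as abnormalities. If the true relationship exists only beyond a threshold, the yes/no test could do as well or better. This is a reason to keep increased ONSD in the report, but not a reason to make it the only form tested.

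The effect sizes and the rate of increased ONSD have no source in the documents. That is so, and the power values are illustrative. At 0.5 SD (14 versus 46) they are 26% versus 15–19%, so either form would usually miss the effect, and the main cause there is a sample size set for another aim. The direction did not change in any scenario run, although all of them assume normality with a shift in the mean.

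Nor does the plan throw the measurement away. The diameter is on the Appendix data list, and continuous variables are to be summarised by mean and SD. The loss is confined to the association tests.

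**Conclusion.** The point holds as a minor, inexpensive improvement. The listed tests of ONSD against albumin, BNP and the severity features use less of the data than is measured. For albumin and BNP, between about one third and two thirds of the information is kept, given normality and 10–50% of patients with increased ONSD. The loss for the severity features is not quantified, because it also depends on how common each feature is, which the documents do not give.

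Separately, one of the three parts of a secondary aim has no listed test and no stated form of ONSD. The fall from 65% to 39–47% shows what would follow if the yes/no form were adopted there and the true difference were 0.8 SD; it is not a property of the plan.

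These are secondary, exploratory analyses. Nothing here touches the primary PIS–LVEDP comparison or the planned 60 evaluable patients.

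**What to change.** In Section F:

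1. Use the continuous mean ONSD in the association tests: a t-test by presence or absence of each severity feature, and correlation or linear regression for albumin and BNP, rank-based if skewed.
2. List PIS versus continuous ONSD, tested with the two-sample t-test already in the plan, and report the mean difference with its 95% CI.
3. Count that comparison in the multiplicity set, stating whether it is already among the 32.
4. Keep increased ONSD as a prevalence with 95% CI and, if wanted, as a supportive yes/no analysis labelled as such.

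The cost is wording, and at most one comparison added to the 32. No new data or patients are needed. A mean difference is less directly usable at the bedside than a yes/no finding, and a true threshold effect could favour the yes/no test; item 4 covers both. Precision for PIS–ONSD remains modest, so the interval should be reported whatever the p-value.

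### One sentence in F) Statistical analysis swaps the two tests, so serum albumin is left with a Chi-square test as its only stated analysis: a minor wording error in an operative rule

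*Combined protocol and SAP*

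**What the plan says.** Section F) Statistical analysis opens by separating variable types in the usual way: "Data will be presented as mean and standard deviation for continuous variables, and frequency and percentage for categorical variables".

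Two consecutive sentences then name the same two tests in the same order.

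- The first compares patients with and without ultrasound abnormalities on "admission systolic and diastolic blood pressures, clinical features of disease severity, and mean BNP levels". It assigns the tests "using 2-sample t-test and the Chi-square test, for continuous and categorical variables respectively".
- The second covers the associations of PIS, increased ONSD or diastolic dysfunction with the clinical severity features, and continues with "serum albumin level, BNP level, and between cardiac and pulmonary ultrasound abnormalities". These "will be explored using the 2-sample t-test and the Chi-square test, for categorical and continuous variables respectively".

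Albumin belongs to a secondary aim in I. Introduction, which is "to explore the association between PIS and ONSD, serum BNP and albumin". In section F albumin is named only in the second sentence. The one biomarker cut-point in the plan is 200 pg/ml for BNP, used for the diagnostic accuracy measures. There is none for albumin.

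The primary association, PIS with raised LVEDP, falls under cardiac versus pulmonary abnormalities and so also appears only in the second sentence. The section Sample size calculation treats it as a comparison of two proportions: the stated number "will be required to detect a significant difference in incidence of PIS between the 2 groups", at 52% versus 15%.

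**The concern.** The second sentence is current, operative text, and it is wrong as written. A 2-sample t-test compares means of a continuous variable. A Chi-square test compares frequencies across categories and takes no account of the order or size of the values that define them.

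Three consequences follow from a literal reading. BNP level gets a t-test in one sentence and a Chi-square test in the next. Albumin gets a Chi-square test and nothing else, with no categories defined to apply it to. The binary primary comparison gets a t-test, although it was sized as two proportions.

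At stake are the power of the albumin and BNP level comparisons if the rule were applied as worded, and the match between plan and report: an analyst who does the sensible thing will have departed from the written rule.

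**Working it through.** **1. The two rules side by side**

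| Item | Preceding sentence | Sentence in question |
|---|---|---|
| Continuous variables | t-test | Chi-square |
| Categorical variables | Chi-square | t-test |
| BNP level | named | named |
| Severity features | named | named |
| Serum albumin | not named | named |
| Cardiac versus pulmonary abnormalities | not named | named |

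**2. The plan's own figure**

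Inputs from Sample size calculation: p1 = 0.52, p2 = 0.15, 15 LVEDP positive and 45 negative (1:3), power 80%, significance level 0.05. Two-sided testing is assumed, since the plan does not state it.

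Pooled proportion: (0.52 + 3 × 0.15)/4 = 0.2425.

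n1 = [1.960 × √(0.2425 × 0.7575 × 4/3) + 0.842 × √(0.52 × 0.48 + 0.15 × 0.85/3)]² / 0.37² = (0.970 + 0.455)² / 0.1369 = 14.8, rounded up to 15.

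So 15 + 45 = 60, as stated. This is a calculation for two proportions, without continuity correction. It fits the conventional mapping (Chi-square for the binary comparison).

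**3. Literal Chi-square on a continuous level, all values distinct**

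The table is 2 × n with one patient per column. With groups n1 and n2, each column holding a group 1 patient contributes n2/n1, and each column holding a group 2 patient contributes n1/n2. The total is n1 × (n2/n1) + n2 × (n1/n2) = n.

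At 15 and 45: 15 × 3 + 45 × (1/3) = 60 on 59 degrees of freedom, p = 0.44. The result is the same whatever the difference between groups. The expected counts are 0.25 and 0.75 per column, so the Chi-square approximation would not be trusted in any case.

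The 15/45 split is also a reasonable stand-in for PIS groups: the plan's rates give 0.52 × 15 + 0.15 × 45 = 14.55 PIS-positive patients of 60.

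**4. The same test with tied values**

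Laboratory values are usually rounded, and ties change the result in step 3. The documents give neither the reporting resolution nor the spread of albumin, so these are assumptions: normal values rounded to whole units, SD 3 to 6 units, groups of 15 and 45, 4,000 simulated samples per setting, two-sided 0.05.

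| True difference | Chi-square on the distinct values | t-test |
|---|---|---|
| 1 SD | about 15% (SD 6) to 32–34% (SD 3; varies between sets of runs) | about 90% |
| 2 SD | about 78% (SD 6) to 97% (SD 3) | about 100% |

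**5. The binary primary comparison**

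For two binary variables, a t-test on 0/1 data and an uncorrected Chi-square test are nearly the same test. Over every possible table at 15/45, 734 can be tested. The two tests reach the same decision at 0.05 in 732 of them. The two exceptions (3/15 versus 22/45, and 12/15 versus 23/45) have p = 0.0494 by Chi-square and 0.0504 by t-test, and are extremely unlikely at the planned rates.

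**The case against.** The strongest reply is that this is an editorial slip with no consequence. The sentence just before it gives the conventional mapping for the same two tests, the opening of the section agrees, and no statistician would run a Chi-square test on raw albumin values. Variable type is fixed before any data are seen, so the slip gives no room to choose a test by its result. Many items in the sentence are yes/no features, for which the two tests nearly coincide. The comparisons that do suffer, albumin and BNP level, are secondary and exploratory, and BNP also has the correct rule in the preceding sentence.

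Most of this stands, and it is why the point is minor. It does not remove the point. The preceding sentence does not name albumin, so its test has to be inferred, and the two sentences contradict each other on BNP.

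A reader might infer two stronger conclusions. The first is that the literal rule could never show an association of PIS with albumin or BNP. That is true only if every value is distinct. With ties, the Chi-square test loses much power but still responds to a difference (step 4). The second is that the primary analysis or its sample size is compromised. The documents do not support this: for a binary table the choice between the two tests makes practically no difference (step 5), and the figure of 60 reproduces from a two-proportion calculation (step 2).

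**Conclusion.** The point holds as a minor wording correction to an operative analysis rule. The contradiction can be read directly from the text and rests on no assumption. That it is a transposition is an inference, though a strong one.

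The cost of following the sentence literally falls on continuous markers, chiefly albumin. The fixed p of 0.44 is a limiting case. The simulated loss, from about 90% to between 15% and one third for a 1-SD difference, depends on the assumed rounding, spread and group split. Both figures describe the rule as worded and do not predict what the study team would do.

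**What to change.** In the second of the two sentences, exchange the words for the two variable types so that it ends as the preceding sentence does: "using 2-sample t-test and the Chi-square test, for continuous and categorical variables respectively". Albumin and BNP levels are then compared by t-test. Binary comparisons, including PIS by raised LVEDP, are made by Chi-square, in line with the sample size calculation.

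The cost is a two-word edit. It changes no sample size or power figure and adds no test.

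### Section F gives two conflicting significance rules (Benjamini-Hochberg at 10% FDR and a fixed p < 0.025), and the sample size uses neither

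*Combined protocol and SAP*

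**What the plan says.** Section F (Statistical analysis) states the multiplicity rule in two consecutive sentences. The first reads: "To adjust for multiple comparisons, including primary and secondary outcomes, a Benjamini-Hochberg correction will be applied using a 10% false discovery rate". The second reads: "Assuming that the p-value will result from 32 direct comparisons made in the study, the significance level will be adjusted to" p < 0.025. The 32 comparisons are not listed, and no derivation of 0.025 is given.

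The Sample size calculation section ties the sizing to the primary comparison: "The sample size calculation is based upon the primary aim, which is to examine the association between PIS on lung ultrasound and raised LVEDP". It arrives at 60 evaluable women (15 with raised and 45 with normal LVEDP) "with a power of 80% and significance level of 0.05", and recruits 70 to allow for poor images. It does not mention the multiplicity correction. Nothing elsewhere exempts the primary comparison from the correction or says which of the two sentences decides significance.

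**The concern.** BH is a step-up procedure: its threshold depends on the observed p-values and cannot be fixed in advance. A fixed cut-off of 0.025 is a different rule with different error properties. An analyst following the plan could apply either and reach different conclusions from the same p-values. Because the choice is open, it could be made after the results are known. With the 32 tests unlisted, the size of the family is open too.

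Separately, Section F places the primary comparison inside the adjusted family, while the sample size assumes it is tested at 0.05. The stated 80% power then does not belong to the test the plan says it will use.

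**Working it through.** **Inputs.** From Section F: m = 32 comparisons, FDR q = 0.10, fixed level 0.025. From the Sample size calculation: PIS rates of 52% (raised LVEDP) and 15% (normal LVEDP), groups of 15 and 45, alpha 0.05, power 80%, recruitment 70. Sidedness is not stated; two-sided is assumed because it reproduces the plan's N.

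**1. BH thresholds.** If k tests are rejected, the threshold is k × 0.10/32 = k × 0.003125.

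| Tests rejected (k) | 1 | 7 | 8 | 10 | 16 | 32 |
|---|---|---|---|---|---|---|
| Threshold | 0.003125 | 0.0219 | 0.025 | 0.03125 | 0.05 | 0.10 |

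The fixed level equals the BH threshold only at k = 8. It is also close to 0.10/Σ(1/i, i = 1..32) = 0.10/4.0585 = 0.0246. The documents support neither origin, and neither would make a fixed cut-off the BH procedure.

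**2. Where decisions differ.**
- p = 0.02: significant at the fixed level. Under BH, 0.02/0.003125 = 6.4, so at least 7 rejections are needed.
- p = 0.03: not significant at the fixed level. Under BH, 0.03/0.003125 = 9.6, so it is significant with at least 10 rejections.

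**3. FDR of the fixed rule.** This is a simulation under assumptions that are not in the documents: 32 independent two-sided z-tests, each real effect with 80% power at 0.025 (mean shift 3.083).

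| Real effects | 1 | 2 | 4 | 6 | 7 | 8 | 16 |
|---|---|---|---|---|---|---|---|
| FDR, fixed 0.025 | 35.3% | 25.1% | 15.4% | 10.5% | 9.0% | 7.8% | 2.8% |
| Studies with at least one discordant test | 57% | 57% | 49% | 33% | – | 21% | 72% |

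BH stays at or below 10% throughout. With 50% power per real effect, the fixed rule's FDR is 42%, 33% and 22% for 1, 2 and 4 real effects, and falls below 10% from about 10. With a common correlation of 0.3 (80% power) it is 29%, 22% and 14%. In the other direction, with 16 real effects the fixed rule finds 80% of them and BH 86%.

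**4. The plan's sample size.** Pooled-variance formula for two proportions, no continuity correction, ratio 1:3:

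- pooled rate = (0.52 × 15 + 0.15 × 45)/60 = 0.2425
- s0 = √[0.2425 × 0.7575 × (1/15 + 1/45)] = 0.1278
- s1 = √[0.52 × 0.48/15 + 0.15 × 0.85/45] = 0.1395
- power = Φ[(0.37 − z × s0)/s1]

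At two-sided 0.05 (z = 1.960) this is Φ(0.857) = 80.4%, and the required N is 15 + 45 = 60, as the plan states. One-sided 0.05 would give 48, and a continuity correction 76.

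**5. The same formula at the levels in Section F, 15 + 45 evaluable.**

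| Level | Power | Exact power, uncorrected chi-square |
|---|---|---|
| 0.003125 (BH, k = 1) | 47.8% | 48.6% |
| 0.025 (fixed; BH, k = 8) | 72.5% | 72.2% |
| 0.05 (BH, k = 16) | 80.4% | 83.0% |
| 0.10 (BH, k = 32) | 87.4% | 88.1% |

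At 0.025, 80% power needs 18 + 54 = 72 evaluable women. If all 70 recruited were evaluable at 1:3, the formula gives 79.1%.

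**6. BH power for the primary, averaged over simulated studies.** The other real effects are as in step 3, and the tests are independent.

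| Other real effects | 0 | 1 | 3 | 7 | 15 | 23 | 31 |
|---|---|---|---|---|---|---|---|
| Power | 49.5% | 54.3% | 62.0% | 70.8% | 79.2% | 83.8% | 86.5% |

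A correlation of 0.3 changes these by about one percentage point at most.

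**The case against.** The strongest reading in the plan's favour is that BH is the operative rule and the 0.025 sentence, being conditional, only anticipates where the BH cut-off will fall; 0.025 is exactly the threshold at eight rejections. That is possible, but the documents do not say it, and the sentence is worded as a decision level. Nor does reading 0.025 as a one-sided equivalent of 0.05 work: it is presented as an adjustment for 32 comparisons, and the chi-square test is non-directional.

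Several points on size do stand:
- The share of studies with any discordant test sounds large, but the mean number of discordant tests is only 0.81, 0.85, 0.72, 0.47, 0.27 and 1.35 out of 32 with 1, 2, 4, 6, 8 and 16 real effects.
- The high FDRs need few real associations. In a single disease with related markers more may be real, though the documents give no number.
- If all 70 women were evaluable, exact chi-square power at 0.025 would be 80.8% (17 + 53) or 81.4% (18 + 52). However, the plan sets the extra 10 aside for poor images, so 60 is the planned evaluable number.
- The 47.8% figure is the worst case, in which no other test is rejected.
- Keeping a primary outcome inside an FDR family is legitimate, so taking it out is partly a preference.
- The study is an observational cohort and describes these associations as exploratory.

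These points limit the consequences. They do not tell the analyst which rule to apply.

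**Conclusion.** The concern holds. Section F contains two incompatible rules, and nothing in the documents reconciles them. Followed literally, the fixed rule misses the stated 10% FDR when few associations are real: about 35% to 15% with one to four, assuming independent tests and 80% power each. When many are real it is stricter than BH. The N of 60 is arithmetically right at two-sided 0.05, but Section F puts the primary comparison under a different level. Power with 60 evaluable is 72.5% at 0.025, and anywhere from 47.8% to 87.4% under BH.

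The thresholds and the power figures by level follow from the plan's own inputs, given two-sided testing. The FDR, discordance and average BH power figures rest on the simulation assumptions stated above. Estimation results (prevalences, confidence intervals, sensitivity, specificity and predictive values) are not touched. This should be fixed before analysis; it does not threaten the study as a whole.

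**What to change.** Before analysis, keep one rule.

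- **If BH is kept:** delete the 0.025 sentence, list in a table the tests that make up m, and state that BH-adjusted p-values for those tests are judged against 0.10.
- **If the fixed 0.025 is kept:** delete the BH sentence, give the origin of 0.025, and state that it does not control the FDR at 10%.

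Then settle the primary PIS–LVEDP test. The simpler choice is to test it alone at two-sided 0.05 and restrict the BH family to the secondary comparisons. This matches the sample size but means amending "To adjust for multiple comparisons, including primary and secondary outcomes". The alternative is to leave it in the adjusted family and restate its power in the Sample size calculation: 72.5% at 0.025 with 60 evaluable (79.1% with 70), or 47.8% to 87.4% under BH, depending on the other p-values.

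The cost is wording, one table and a line of code. No new patients are needed unless 80% power at 0.025 is wanted, which takes 72 evaluable instead of 60. Each choice has a downside:
- Under BH, some results with p between 0.003 and 0.025 lose significance when few tests are positive.
- A primary left in BH could be declared positive at a raw p above 0.05. In simulation this occurs in 0.2%, 3.4% and 6.2% of studies with 15, 23 and 31 other real effects.
- A primary tested alone is outside the FDR control.
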